There has been an exponential increase in the number of day case surgical procedures also called as ambulatory surgeries (AS), over the last 2 years.⁽¹⁾ Currently around 70% of procedures are being done as AS, with known benefits to patients and hospitals.⁽²⁾ Its efficiency and cost effectiveness depends upon its organization and delivery of services. Pain and PONV are recognized as the leading factors affecting the quality of services delivered under AS,^(1,3) and they affect the recovery, discharge, and overall satisfaction of patients.^(4,5) According to literature, postsurgical pain could be inadequately treated in 30%-60% of patients and 30%-40% of AS patients suffer from significant PONV.^(3,6,7) It is estimated that a single episode of PONV can prolong the PACU stay by 25 mins,⁽⁸⁾ and patients rate PONV to be the most undesirable outcome associated with anesthesia.⁽⁴⁾ Despite the increasing use of non-opioid analgesics, opioid analgesics have remained the primary modality in moderate to severe pain.⁽⁷⁾ They cause several side effects such as drowsiness, sedation, PONV, itching and respiratory depression. Appropriate selection of opioid medications becomes significantly important to deliver safe and effective analgesia with minimal side effects. Although M has been the most commonly used medication, HM is also being increasingly used.⁽⁹⁾ We do not yet know whether HM is more effective than M in AS patients. Both M and HM exert no ceiling effect for their analgesia, and by this nature incomplete or inadequate analgesia is related to the appearance of side effects.⁽¹⁰⁾ Hence clinical effectiveness of opioids, relative to each other, is reflected not just by satisfactory analgesia, but by a combination of 'satisfactory analgesia with limited side effects'. Clinical observation suggests that HM is clinically better by providing superior or equivalent analgesia with decreased side effects.⁽⁹⁾ HM is a semi-synthetic morphine derivative that differs from M in its position 6 of the benzol ring, where it has a keto-group instead of a hydroxy group, making it

Most Effective Opioid Analgesia in Ambulatory Surgeries: a randomized control, investigator blinded, parallel group with superiority design study of Morphine versus Hydromorphone

[name], Principal Investigator SJHH

[name], Principal Investigator HHS

5–10 times more potent and enhances its distribution to cerebral tissues, making for easier titration.⁽⁹⁾ The t_{1/2} Ke0 (transfer life from plasma to effect site) is 1.6hr – 4 hr for M, compared to 18-38 min for HM.^(9,10) It is observed that health care providers may be willing to provide higher dose of HM compared to M in EMU, as its actual quantity of drug is much smaller and therefore appears to cause less concern.^(12, 13) Our literature review showed that there are no previous studies comparing these 2 medications in AS patients. The lone systematic review compared various acute and chronic pain studies, in various routes of drug administration.⁽⁹⁾ Of the 11 studies identified; only 4 were done in acute pain settings.⁽¹³⁻¹⁶⁾ Two of them were done by the same author in ER settings. Chang et al noted that HM reduced the mean pain scores by 1.3 units [95% CI= (-2.2 to -0.5)] compared to M in 198 adults treated in ER.^(12,13). However it did not show much difference in geriatric population.¹⁴ In perioperative settings, Hong et al studied the difference in nausea between the 2 medications in 50 patients using PCA and found no difference.⁽¹⁵⁾ Rapp et al studied various effects between the 2 medications in 61 surgical patients using PCA. There is not much clarity about their primary outcome; however they found the effects to be similar.⁽¹⁶⁾ Both these studies had smaller sample sizes. The meta-analysis performed demonstrated that the HM does provide better analgesia than M, with a small effect size; Cohen's d=0.266 (p=0.012).⁽⁹⁾ Looked at acute pain alone it was statistically significant (p=0.006), compared to chronic pain (p=0.889). It was noted that that there is a definite lack of comparative studies between them in surgical settings.

Patients Symptoms after Discharge

It is being appreciated that, research and health care delivery have not focussed much on the post discharge symptoms after day surgeries. In this direction, two crucial aspects are to be considered. Compared to inpatients, ambulatory surgery patients have less efficient access to health services.⁽¹⁸⁾ It is wrong to assume that the burden of pain, nausea and other symptoms, after ambulatory surgery patients, is not substantial. A significant number of patients suffer from continuing pain even at 24 hours, or a week after surgery.⁽¹⁹⁾ Up to 1/3rd or more number of patients suffer from nausea or vomiting after surgery. Studies have shown that differences in anesthetic management, and choice of medications (even with non-analgesic medications such as propofol or sevoflurane) have made a difference in patient's perception of pain in ambulatory surgeries in the first 24 hrs, and beyond.⁽¹⁹⁾ A systematic review noted that only around 30%-42% of studies on ambulatory surgery patients, assessed for pain, nausea, and vomiting after discharge.⁽²⁰⁾ Due to significant heterogeneity, and study limitations, appropriate figures of observed incidence could not be calculated. Several of the included studies were also not well designed. Similarly, day surgery patients can also suffer from chronic postsurgical pain (CSPS), at 1 year or more after surgeries. It has been observed that up to 10%-50% patients, and 2%-11%

Most Effective Opioid Analgesia in Ambulatory Surgeries: a randomized control, investigator blinded, parallel group with superiority design study of Morphine versus Hydromorphone

[name], Principal Investigator SJHH

[name], Principal Investigator HHS

patients, suffer from moderate and severe level of CPSP.⁽²¹⁾ The definition of CPSP, in terms of the duration after surgery, has not been clearly identified. However, persistence beyond 2 months is normally considered as CPSP.⁽²²⁾ Specific to day surgeries, not many studies have assessed the incidence of CPSP and its predictive factors. A recent, large observational study, involving 908 patients, observed a CPSP (moderate to severe) rate of 15.3% after day surgeries.⁽²³⁾ They found that surgical specialty, preoperative pain, preoperative analgesic use, acute postoperative pain, surgical fear, lack of optimism and poor preoperative quality of life, as factors predictive of CPSP.

Hence, we will also look for any differences in pain, nausea and vomiting over the first 24 hrs after the surgery, along with chances of readmission or ER visits within the same period, post discharge. At 3 months, we will look for the incidence of persisting pain after surgery.

Hypothesis

In patients who undergo ambulatory surgical procedures causing at least moderate pain, hydromorphone (HM) increases the proportion of patients who would demonstrate 'satisfactory analgesia [$=<4/10$ NAS] with minimal or no postoperative nausea-vomiting (PONV) [$<2/5$ VDS] as compared to morphine (M), when both are administered intravenously, in equianalgesic doses, and are compared at 2 hours after surgery in PACU.

2. Specific Objectives

The primary objective of this study is to compare the proportion of patients with SAME (satisfactory analgesia and minimal emesis) after AS, when using M compared with HM, during the immediate postoperative hospital stay.

Secondary objectives include:

1. Total dose of analgesic used in PACU, in morphine equivalents,
2. Time to discharge or readiness to discharge from the DSU,
3. Proportion of pain, and its comparison after discharge, within 24 hours,
4. Proportion of nausea, and its comparison after discharge, within 24 hours,
5. Proportion of vomiting, and its comparison after discharge, within 24 hours,
6. Incidence of CPSP at 3 months after discharge

The tertiary objectives include:

1. Proportion of patients with severe itching,

Protocol Version Date: Version 5 / June 23, 2015

Most Effective Opioid Analgesia in Ambulatory Surgeries: a randomized control, investigator blinded, parallel group with superiority design study of Morphine versus Hydromorphone

[name], Principal Investigator SJHH

[name], Principal Investigator HHS

2. Proportion of patients with significant sedation,
3. Proportion of patients with significant respiratory depression,
4. Patient satisfaction score at the time of discharge,
5. Time to discharge or readiness to discharge from the PACU,
6. Use of ketorolac as a rescue medication,

METHODS

The study is designed as a multisite, 2 arm, parallel, superiority design with randomization of patients and blinding of patients, health care providers (physicians and nurses) and research personnel (research coordinator and data analyst). Patients will be stratified based on site and laparoscopic/open surgeries. Intention to treat approach will be used for design and analysis.

Patient Selection and Recruitment: Patients', who undergo AS of the abdominal and pelvic regions, within the scope of general surgical (GS), gastrointestinal (GI) and gynecological (GYN) specialties, shall be considered. Patients shall be considered for the study if they fulfill the following selection criteria. They would be screened on the day of their preoperative appointment, assessed for eligibility and then if they agree, obtain consent.

The inclusion criteria will include: age 18 yrs to 70 yrs-; ambulatory surgeries producing at least moderate pain-such as cholecystectomy, appendectomy, ovarian cystectomy, inguinal hernia repair, abdominal wall hernias; and an ability to communicate in English.

Exclusion criteria will include: allergy to M or HM; patient on regular chronic opioid medication; patient uncontrolled systemic disease; severe obesity with a BMI >35; significant psychological impairment; history of drug addiction or dependence; any planned regional or nerve block other than local anesthesia infiltration; patients with confirmed sleep apnea; emergency surgeries and urological surgeries.

Suitable patients will be screened before their visit to 'pre-anesthetic visit'. During their visit, they will be approached by a trained RA, involved with the study. Relevant information will be provided, along with a letter of information about the research study. Consent of willing patients will be obtained, along with their baseline, and demographic variables. The consent will include the study process, and also willingness to be followed, and contacted at 24 hours and at 3 months after surgery.

On the day of surgery, at DSU, patients' consent will be confirmed. Relevant baseline variables of the recruited patients shall be noted (appendix 1). The concerned OR anesthesiologist is informed of the patient's inclusion to the study and reinforced about the study methodology (appendix 2).

Most Effective Opioid Analgesia in Ambulatory Surgeries: a randomized control, investigator blinded, parallel group with superiority design study of Morphine versus Hydromorphone

[name], Principal Investigator SJHH

[name], Principal Investigator HHS

Allocation and Randomization: Treatment allocation will be done using a random, computer generated table, with an allocation ratio of 1:1, using random permuted block sizes. Stratification based on each centre (3 sites). These syringes (4*10 mls)-in sealed packages, labelled with serial numbers and no identifiers for the medication, shall be deposited in a safe drug locker, within the fridge, at the respective PACU. The actual randomization, for each patient happens as they enter into the PACU after surgery. The PACU nurse allotted for that patient will obtain the next medication package in series to be used for that patient. To ensure that the respective patient and medication is matched for subsequent analysis, the nurse will attach the medication sequence number on the patient study records, with no identifiers of actual drug. The PACU nurse shall also note down the patient hospital ID on the medication syringe, once it is taken out, to ensure there is no mix up.

Blinding: The study allocation will be blinded to patients, treating nurses, physicians, research assistant and investigators. The allocation order will be available only to the person responsible for randomizing and the pharmacists involved in the study at each centre.

Application of Intervention:

The Operating Room Protocol: Patients included in the study need to be managed according the OR protocol provided in Appendix 2. In brief, the patient will only have a GA, with local infiltration provided at the end of the surgery. Long acting opioid medications (morphine and hydromorphone) are not administered in the OR. LA infiltration is done within a range of 20-30 mls (based on laparoscopic or open surgeries) using 0.25% bupivacaine with or without adrenaline.

PACU Stay: The actual study intervention (hence randomization) will only become applicable once the patient is moved to the PACU. Every patient will be treated as per the protocol during the intraoperative management, which primarily restricts the use of any study opioids. The details are provided in appendix 2. The nurse looking after the study patient in PACU will administer the medication as per the study protocol. This would include analgesia with equipotent doses of M or HM administered in titrated doses. Syringes will be pre-prepared from the pharmacy in EMUs; 1ml=1mg of morphine or 0.2 mg of hydromorphone. We shall consider a potency ratio of 1:5 (M: HM), considered equivalent in literature.⁽⁹⁾ Analgesia will be provided according to the following guideline. A similar method has been advised to be safe and effective for titrated analgesia in PACU.⁽²⁴⁾ Readiness to discharge from PACU and outcomes are noted at 2 hrs, or at the time of discharge to DSU.

Most Effective Opioid Analgesia in Ambulatory Surgeries: a randomized control, investigator blinded, parallel group with superiority design study of Morphine versus Hydromorphone
[name], Principal Investigator SJHH
[name], Principal Investigator HHS

PACU Protocol (titrate the opioid medication to achieve desired pain score)

- Patient to be asked for their pain score, and if it is more than 4 out of 10 (NAS): to receive the 1st dose within 5 minutes after coming to PACU: 0.04mg/kg morphine units (rounding off to the nearest 1 ml or 0.5 ml); with a maximum of 3 mg of morphine equivalents.
- Repeat doses: 0.02 mg/kg morphine units every 5-10 minutes to titrate for analgesia and side effects (rounding off to the nearest 1 ml or 0.5 ml)
- If no side effects observed-titrate to have analgesia: NAS =<4/10.
- If Nausea-Vomiting observed: record it in the CRF provided and treat it with antiemetics (Ondansetron 1-4 mg IV, Dimenhydrinate 25-50 mg)
- If patient is too sedated (<3-Ramsey Sedation Scale)-withhold the next dose and restart the bolus if the score is >3
- If respiratory depression present, withhold the next dose, treat with Naloxone if necessary.
- Ketorolac IV 15-30 mg as rescue medication if patient does not tolerate the study opioid or if the patient does not satisfy the success of satisfactory analgesia at more than 1 hr.

DSU Stay and Protocol:

At the end of 2 hours or after satisfactory completion of primary endpoints, patients shall be transferred to DSU. At the DSU, in both groups, patients shall be given oral Oxycocet (combination of oxycodone and paracetamol) or Tylenol 3 (combination of codeine and paracetamol), as a PRN medication, if necessitated by the patient's pain. Nurses shall note down the occurrence of any pain and nausea necessitating treatment in the patient's CRF. Readiness to discharge home is noted down for each patient. The RA shall collect the CRFs from PACU and DSU and deposit safely in a locked filing cabinet.

Planned Outcomes: Our combined primary outcome will be proportion of patients with SAME, as compared between the 2 groups. Analgesia will be based on NAS 0-10 (appendix 3), and PONV will be based on VDS 0-5 (appendix 3). These observations will be made at the end of 2 hrs or before (corresponding to the time of discharge from PACU), by the PACU nurse, in the specified CRF. All the other outcomes to be recorded within the hospital, along with the time of their measurement and proposed analysis method are noted in table 1.

Sample Size Calculation: It was calculated based on the primary, binary outcome of proportion of patients with SAME, which will be compared using a chi-square test. According to literature,

Most Effective Opioid Analgesia in Ambulatory Surgeries: a randomized control, investigator blinded, parallel group with superiority design study of Morphine versus Hydromorphone
 [name], Principal Investigator SJHH
 [name], Principal Investigator HHS

approximately 30%-40% of patients are provided with inadequate analgesia after their AS,^(25, 26) with a similar number also known to suffer from PONV after AS.^(3, 24) Our chart reviews suggests that approximately 20% of patients suffer from inadequate analgesia with PONV using morphine. For a 2-sided test, with an alpha of 0.05 and a power of 90%, and with an estimated effect size of 10% (p1= 80% and p2= 90%), a sample size of 266 per group was calculated. However, for recruitment we shall have a target of 275 per group, for a total of 550 patients (rounding off). For the primary outcome analysis, we expect minimal loss through attrition as the study involves a follow up of few hours. The expected recruitment is approximately 20 cases per month at each of the 3 sites. We expect the trial to run for 10-12 months.

Table 1: Study Outcomes, and their Measurement and Analysis

OUTCOME MEASURE	TYPE	MEASUREMENT	TIME OF MEASUREMENT	ANALYSIS METHOD
Primary outcome Satisfactory Analgesia with minimal PONV	Binary	NAS=<4/10 VDS<2/5	At 2hrs or at the time of discharge from PACU	Chi-square
Severe Itching	Binary	VAS>5/10	At 2hrs or at the time of discharge from PACU	Chi-square or Fisher's test (as appropriate)
Severe Sedation	Binary	Ramsey Score >3/6	At 2hrs or at the time of discharge from PACU	Chi-Square or Fisher's test (as appropriate)
Severe Respiratory Depression	Count	All cases needing treatment as counts	At 2hrs or at the time of discharge from PACU	Chi-square or Fisher's test (as appropriate)
Use of Ketorolac	Continuous	Total dose used per patients as a rescue therapy	At 2hrs or at the time of discharge from PACU	T test
Mean dose of Analgesic Used	Continuous	Dose of Analgesic used per patient in EMU	At the time of hospital discharge	T test

Most Effective Opioid Analgesia in Ambulatory Surgeries: a randomized control, investigator blinded, parallel group with superiority design study of Morphine versus Hydromorphone
 [name], Principal Investigator SJHH
 [name], Principal Investigator HHS

Patient Satisfaction-Mean score (0-10)	Continuous	Mean Score calculated between 0 to 5 scale	At the time of hospital discharge	T test
Time to discharge from PACU	Continuous	Mean time in hrs	At 2hrs or at the time of discharge from PACU	T test
Time to discharge from the hospital	Continuous	Mean time in hrs	At the time of hospital discharge	T test

Outcomes at Post-operative Day 1:

Patients will be approached by 1-2 phone calls shall be done during the next day; if unanswered, a repeat call will be made on the subsequent day (2nd day after discharge); for responders, the following questions will be asked.

1. What was your average pain score over the last 24 hrs, in 0-10 NAS scale, after you were discharged home?
2. After discharge, did you have nausea-severe enough to require medications at home?
3. After discharge, did you have vomiting-severe enough to require medications at home?
4. After discharged home, did you require a visit to ER, or readmission?

Outcomes at 3 months:

Patients will be contacted by a mailed package at 3 months after surgery to collect the following outcomes.

1	Do you have Persistent Pain (which started with or after surgery), at or near the surgical area?	Yes or No
2	Intensity of Pain	NAS: 0-10
3	Brief Pain Inventory-Interference Items 7 Items: each item scored between 0-10	
4	Global Impression of Change	Likert scale 1-7

Most Effective Opioid Analgesia in Ambulatory Surgeries: a randomized control, investigator blinded, parallel group with superiority design study of Morphine versus Hydromorphone
[name], Principal Investigator SJHH
[name], Principal Investigator HHS

5	Analgesic Use: Did you have to use any pain medications for more than 1 month, to help with pain, which started with or after Surgery?	Yes or No
---	---	-----------

Statistical Analysis: The study will be analyzed using an intention to treat approach. The individual outcomes along with their respective analyses method have been listed within the table 1. Broadly the dichotomous outcomes will be reported as proportions and analyzed using a chi-square test to detect a significant difference ($p<0.05$). Precision will be reported using 95% CI. Continuous outcomes will be analyzed using an unpaired 2-tailed student t test for significance ($p<0.05$). Means and standard deviations shall be reported along with 95% CI. We also plan to perform logistic multivariable regression analysis to account for the influence of baseline covariates, which are listed in appendix 1. A sensitivity analysis will be performed to compare the effects of laparoscopic surgeries vs open surgeries.

Trial Management: This trial will be conducted at 3 hospital sites affiliated with McMaster University, Hamilton: St Joseph's Hospital, McMaster University Hospital and Juravinski Hospital.

Data Management and Quality Control: All study data including CRFs of each patient, shall be securely stored at the central office. A summary table indicating study timeline from enrollment to final follow-up (<http://www.spirit-statement.org/title/>) shall be included for each patient.⁽²⁷⁾ CRF's will be collected as paper forms. They shall be periodically cross-checked for completeness and entered into a suitable electronic master file. All reports of incorrect randomizations, protocol violations or incomplete data shall be noted.

Risk Assessment and Protocol Adherence: This trial does not entail any higher risk than the standard of care to the patients. This is a pragmatic trial and involves the use of medications of known benefit and in clinically acceptable doses. It also involves using only short acting opioids in the form of fentanyl or sufentanil or remifentanil in small boluses or infusion. Although for some this might differ from their normal practice, we do not anticipate this to be a major issue as the surgeries would be of 1-2 hrs duration and can be effectively and safely managed with short acting opioids until patients are shifted to PACU. Protocol also involves the use of study medications in PACU at an initial dose of 0.05mg/kg, followed by 0.03/mg/kg EMU boluses. Studies have shown that IV Morphine titration in PACU, after moderately painful surgeries

Most Effective Opioid Analgesia in Ambulatory Surgeries: a randomized control, investigator blinded, parallel group with superiority design study of Morphine versus Hydromorphone

[name], Principal Investigator SJHH

[name], Principal Investigator HHS

require a mean morphine dose of $0.17 +/ - 0.10$ mg/kg.^(17,28) Only doses as high as 0.15mg/kg were found to be associated with significant adverse effects.⁽²⁹⁾

Potential Pitfalls (Study Limitations): Despite being a randomized study, there exists the possibility of bias due to unequal distribution of unknown covariates. The primary outcome of SAME is being measured using subjective pain scale of NAS and VDS for emesis. Although there are inherent limitations of such scales, we think they are widely used in practice and are well validated. We have considered a potency ratio of 1: 5 (M: HM) as it is commonly used and supported by the literature. However, we do accept that there is a much wider range described in some studies.

STUDY SIGNIFICANCE:

The potential impact of the study could change the routine practice for anesthesiologists and other care providers. By choosing a better medication, physicians can be confident of their choice based on clear evidence, instead of a trial and error method in PACU management which usually leads to increased time with inferior results. The perceived advantages include better analgesia, less side effects, early discharge, reduced use of medications, less overall cost, and better patient satisfaction. These are truly reflective of what are proposed to be the most ideal outcomes for AS setting.⁽²⁾ These results could facilitate early discharge will require lesser costs due to savings on manpower. The study will also provide an estimate of incidence of pain, nausea and vomiting after discharge, within the first 24 hrs after surgery. The burden of such a problem will help to organize better health service provision in future, for patients of day surgeries. The study will also give us an indication of incidence of persistent postoperative pain; and also whether better control of their acute pain makes an impact on the incidence and severity of persistent pain at 3 months.

Most Effective Opioid Analgesia in Ambulatory Surgeries: a randomized control, investigator blinded, parallel group with superiority design study of Morphine versus Hydromorphone
[name], Principal Investigator SJHH
[name], Principal Investigator HHS

REFERENCES

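### Secondary objective 3 compares a proportion with pain in the first 24 hours, but only an average 0-10 score is collected and no cut-off is set; the score itself should be the outcome

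*Combined protocol and SAP*

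**What the plan says.** In section 2, Specific Objectives, secondary objective 3 reads "Proportion of pain, and its comparison after discharge, within 24 hours". Objectives 4 and 5 use the same form for nausea and vomiting.

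The data come from the telephone call described under Outcomes at Post-operative Day 1 and repeated in the Appendix 1 case record form. The pain item is "What was your average pain score over the last 24 hrs, in 0-10 NAS scale, after you were discharged home", which yields a number. The nausea item is "After discharge, did you have nausea-severe enough to require medications at home", a yes/no question with its severity threshold built in, and the vomiting item is parallel. Objectives 4 and 5 can therefore be computed as worded. Objective 3 cannot.

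The Statistical Analysis section states that "The individual outcomes along with their respective analyses method have been listed within the table 1". Table 1, however, is introduced under Planned Outcomes with "All the other outcomes to be recorded within the hospital, along with the time of their measurement and proposed analysis method are noted in table". It covers in-hospital outcomes and has no row for 24-hour pain. Two general rules remain. One is "Broadly the dichotomous outcomes will be reported as proportions and analyzed using a chi-square test"; the other sends continuous outcomes to an unpaired two-sided t test, with means, SDs and 95% CIs.

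The only pain cut-off on the NAS is 4 out of 10. It appears in the Table 1 primary-outcome row ("NAS=<4/10 VDS<2/5"), in the Hypothesis and in the PACU Protocol. All three concern the PACU, and nothing extends the cut-off to the call at home.

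**The concern.** The objective's wording points to the chi-square rule, while the instrument points to the t-test rule. If the wording governs, someone must decide which score counts as pain, and the protocol does not say who decides, when, or at what value.

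This has two consequences. First, cutting a 0-10 score into two groups throws away information that has already been collected, and the amount depends on where the cut falls. Second, if the threshold is still open when outcomes by arm can be seen, the reported p-value no longer has its nominal meaning.

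The outcome matters to the trial's stated aims. The protocol gives symptoms after discharge their own rationale section, and Study Significance names the 24-hour burden as a product of the trial.

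**Working it through.** **Inputs from the protocol.** Target of 275 per group, two-sided alpha 0.05, and 80% v 90% at 90% power for the primary outcome (Sample Size Calculation). Standardised effect d = 0.266 (introductory literature review), which is a pooled analgesia effect.

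**Assumptions, because the documents give no figures.** A roughly normal 24-hour score with mean 3-5 and SD 2-2.5, rounded to whole points and limited to 0-10. Non-response to the call is shown at 0% and 20%.

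**1. The plan's own figure.** No power is stated for 24-hour pain. For the primary outcome, with pooled variance and mean proportion 0.85:

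n = [1.96·√(2·0.85·0.15) + 1.2816·√(0.16 + 0.09)]² / 0.10² = (0.990 + 0.641)² / 0.01 ≈ 265.9, so 266 per group.

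This matches the protocol.

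**2. Information kept after a cut.** For a normal shift, the efficiency of the dichotomised score relative to the full score is φ(z_p)² / [p(1 − p)], where p is the share counted as having pain.

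| Share with pain | Calculation | Kept | Lost |
|---|---|---|---|
| 50% | 0.3989² / 0.25 | 64% | 36% |
| 70% | 0.3477² / 0.21 | 58% | 42% |
| 80% | as above | 49% | 51% |
| 90% | 0.1755² / 0.09 | 34% | 66% |
| 95% | as above | 22% | 78% |

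The loss passes one half at p ≈ 0.79, or by symmetry at p ≈ 0.21. These figures do not depend on d. At an even split, 550 patients are worth 550 × 0.637 ≈ 350; at 90/10 they are worth 550 × 0.342 ≈ 188.

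**3. Where particular cuts would fall.** After rounding, P(score > 0) = Φ((mean − 0.5)/SD).
- Lowest, mean 3 and SD 2.5: Φ(1.00) = 84%.
- Highest, mean 5 and SD 2: Φ(2.25) = 99%.

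At every mean and SD in the assumed range, a cut at any pain lies beyond 79/21 and loses 56-92% of the information.

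For the trial's existing cut, P(score > 4) = Φ((mean − 4.5)/SD). This runs from Φ(−0.75) = 23% (mean 3, SD 2) to Φ(0.25) = 60% (mean 5, SD 2), with a loss of 37-48%.

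**4. Threshold chosen after seeing the data.** Simulation under no treatment effect, 275 per arm, 10,000 runs per setting. Taking the best of three cuts (>3, >4, >5) rejects in about 11-12% of trials. The best of five (adding >0 and >6) rejects in about 18-20%. The comparison of means stays at about 5%.

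**5. Power, for illustration only** (normal approximation). For the score, power = Φ(d·√(n/2) − 1.96). At d = 0.266 and n = 275 this is Φ(3.119 − 1.96) = 88%. For the cut score, the two proportions are p and Φ(z_p − d), compared by the pooled two-proportion test.

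| d | n per arm | Mean score | 50/50 cut | 90/10 cut |
|---|---|---|---|---|
| 0.266 | 275 | 88% | 70% | 49% |
| 0.266 | 220 (20% not reached) | 80% | 60% | 41% |
| 0.15 | 275 | 42% | 29% | 19% |
| 0.10 | 275 | 22% | 15% | 10% |

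**The case against.** The strongest reply is that the plan does not oblige anyone to lose information. The full score is collected, and the general rule for continuous outcomes could be applied to it as it stands. The text before the Hypothesis also speaks more loosely of looking for any differences in pain. Alternatively, the PACU cut-off could be carried over before unblinding; patients, investigators and the data analyst are all blinded. This stands. A reader might infer that the outcome must either sit at ceiling or be cut after the data are seen, or that the score will be discarded. The documents support neither inference: other routes are open, but none is written down.

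A reader might also infer that most of the information is lost. That is true only beyond about 79/21; a mid-scale cut keeps more than half. The near-ceiling result for any pain rests on assumed means and SDs. Eligibility is limited to surgery expected to be at least moderately painful, which makes the result plausible but does not establish it.

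Nor do the documents show that a well-powered test is being spoiled. The d of 0.266 comes from a review that mixed acute and chronic pain and several routes of administration. Here both arms are titrated to the same pain target in PACU and then have the same oral analgesics available, so a smaller difference at home is plausible. Absolute power may then be low under either analysis. The relative loss remains.

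Finally, a proportion has a purpose: Study Significance promises an estimate of how often pain occurs after discharge. That justifies reporting a proportion with a defined cut-off. It does not require the comparison between arms to rest on it.

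**Conclusion.** The point holds in a limited form. Objective 3 cannot be computed as worded, because it asks for a proportion from a 0-10 score without a threshold, and no analysis is assigned to it. Following the wording would cost about 36-42% of the information at cuts between 50/50 and 70/30, and more than half only at more extreme cuts. A threshold at any pain would be one of those under the assumed means and SDs. An open threshold also carries a risk of inflated type I error, to about 11-12% with three candidate cuts, if it is chosen with outcomes by arm in view; nothing in the documents says that this would happen.

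The efficiency figures assume a roughly normal score with a shift between arms. The power figures depend on an effect size not estimated for this outcome and serve as illustration only. This is a secondary outcome. The primary analysis and its sample size are unaffected. The change is worth making because it recovers information already collected and closes the choice of threshold.

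**What to change.** - Reword secondary objective 3 as the between-group difference in average pain score (NAS 0-10) after discharge, within 24 hours.
- Analyse it as a mean difference with 95% CI, by the t test that Statistical Analysis already prescribes for continuous outcomes.
- Add a row to Table 1 for this outcome, giving its type, source question, time and method.
- Keep one supporting proportion at the cut the trial already uses (NAS >4), fixed in writing before unblinding, to serve the incidence aim in Study Significance.

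The cost is the wording of one objective and one table row. No new data, patient contact or change in patient management is needed. The only thing given up is the proportion's place as the main comparison, since it becomes supportive.
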